In P007, at the same doses (16 mg and 24 mg), preliminary data from Panels A (healthy participants) and B (participants with schizophrenia) suggest that MK-8189 exposure appeared to be greater in participants with schizophrenia when compared with healthy participants; 1.6 - 2-fold and 1.5 - 1.7-fold for AUC0-24 and Cmax values, respectively at the 16 and 24 mg dose. However, when PK data from participants with schizophrenia dosed in Panel C (add-on therapy) and Panel D (monotherapy) were compared with Panel A, PK data were similar between healthy participants and participants with schizophrenia; the reason for the higher exposure observed in Panel B is currently unknown. CL/F (CV%) was found to be 3.65 L/hr (67%) with half-life (CV%) found to be 8.33 hr (21%).

## 2.3 Benefit/Risk Assessment

Healthy participants and participants with hepatic impairment in this trial will not receive direct benefit from treatment during participation as clinical studies are designed to provide information about the safety and effectiveness of an investigational medicine.

Additional details regarding specific benefits and risks for participants participating in this clinical study may be found in the accompanying IB and informed consent documents.

### 3 HYPOTHESES, OBJECTIVES, AND ENDPOINTS

The study population includes male and female participants with moderate and mild hepatic impairment between the ages of 18 and 75 (inclusive) and healthy controls.

Objectives	Endpoints
Primary	
Part 1 

• To compare MK-8189 pharmacokinetics after single dose administration of 4 mg MK-8189 to participants with moderate hepatic impairment and healthy control participants.

• Estimation: The AUC0-inf and Cmax in participants with moderate hepatic impairment will be estimated and compared to those obtained from healthy control participants.

	Part 1 and Part 2 

• AUC0-inf and Cmax

Part 2 

• To compare MK-8189 pharmacokinetics after single dose administration of 4 mg MK-8189 to participants with mild hepatic impairment and healthy control participants.

• Estimation: The AUC0-inf and Cmax in participants with mild hepatic impairment will be estimated and compared to those obtained from healthy control participants in Part 1.

	

Objectives	Endpoints
Secondary	
Part 1 

To evaluate the safety and tolerability of MK-8189 in patients with moderate hepatic impairment and in healthy control participants after single dose administration of 4 mg MK-8189.

	Part 1 and Part 2 

Adverse experiences, laboratory safety tests, electrocardiograms and vital signs

Part 2 

To evaluate the safety and tolerability of MK-8189 in patients with mild hepatic impairment after single dose administration of 4 mg MK-8189.

	
Tertiary/Exploratory	
Part 1 and Part 2 

To investigate the relationship between CYP2C9 genetic polymorphisms and the PK of MK-8189. Genetic variation in CYP2C9 may be analyzed for association with any laboratory or clinical data collected in this study.

To explore the relationship between genetic variation and response to the treatment administered, and mechanisms of disease. Variation across the human genome may be analyzed for association with clinical data collected in this study.

To compare additional MK-8189 pharmacokinetic parameter values after single dose administration of 4 mg MK-8189 to participants with moderate hepatic impairment, mild hepatic impairment, and healthy control participants.

	Part 1 and Part 2 

Germline genetic variation in CYP2C9 and association to clinical data collected in this study

Germline genetic variation and association to clinical data collected in this study.

AUC0-24, C24, Tmax, CL/F, Vz/F and apparent terminal <math>t_{1/2}</math>

## 4 STUDY DESIGN

### 4.1 Overall Design

This is a 2-part, non-randomized, open-label, single-dose study to compare, in Part 1, the PK of MK-8189 in participants with moderate hepatic impairment (based on the Child-Pugh classification) to healthy control participants reasonably matched to the demographics (age, weight, sex) of the group with hepatic impairment. Following a review of the safety and PK data from Part 1, a decision will be made as to whether Part 2 will be initiated; if there is a clinically meaningful higher exposure of MK-8189 in participants with hepatic impairment as compared to healthy participants, Part 2 will be conducted. Part 2 of the study will compare the PK of MK-8189 in participants with mild hepatic impairment to the healthy participants enrolled in Part 1. On Day 1, a single oral dose of MK-8189 will be administered and followed by PK sampling for 96 hours in the healthy control participants and for 120 hours in the mild and moderate hepatic impaired participants. Safety will be monitored through physical examination, vital signs, 12-lead electrocardiograms (ECGs), adverse events and clinical laboratory tests.

The clinic will attempt to contact participants (including participants who terminate the study early) using their standard procedures approximately 14 days after study drug administration to determine if any adverse events have occurred since dosing.

In Part 1, a total of up to 16 adults male and female participants will be enrolled. Up to 8 participants with moderate hepatic impairment (a score of 7 to 9, on the Child-Pugh scale) and up to 8 healthy control participants matched to the mean demographic of the moderate hepatic impairment group (see Section 5 for matching criteria).

In Part 2, up to 8 participants with mild hepatic impairment (a score of 5 to 6 on the Child-Pugh scale) will be enrolled. The healthy control group in Part 1 will be used for the PK comparison in Part 2.

Because this is a Phase 1 assessment of MK-8189 in humans, the PK, pharmacodynamic, and safety profiles of the compound are still being elucidated. This protocol is therefore written with flexibility to accommodate the inherent dynamic nature of Phase 1 clinical studies. Refer to Section 8.11.6 for examples of modifications permitted within the protocol parameters.

Specific procedures to be performed during the study, as well as their prescribed times and associated visit windows, are outlined in the SoA in Section 1.3. Details of each procedure are provided in Section 8.

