### 4.2 Scientific Rationale for Study Design

A 2-part, open-label study design has been selected to evaluate the effect of hepatic impairment on the PK of MK-8189. Though hepatic elimination may be important for MK-8189, the magnitude of the preclinical and clinical safety margins support a reduced design with an evaluation of participants with moderate hepatic impairment first; in the clinic a

starting dose 2-fold and a top dose 12-fold the proposed dose have been evaluated and found to be generally well tolerated (Panel D, P007). It has been recognized that, in general, low clearance compounds ( $CL < 20$  L/h) are less affected by hepatic impairment [Heimbach, T., et al 2020]. Though MK-8189 is primarily eliminated through hepatic metabolism, the low clearance of MK-8189 ( $CL/F < 5$  L/hr) may limit the effect of moderate hepatic impairment on MK-8189 PK.

Following a review of the safety and PK data from moderately hepatic impaired patients and healthy control participants (Part 1), a decision will be made by the Sponsor whether to conduct Part 2 in mildly hepatic impaired participants. If a clinically meaningful increase in MK-8189 exposure is observed in participants with moderate hepatic impairment (Part 1) when compared to healthy participants, Part 2 will be initiated. The effect of mild hepatic impairment on MK-8189 PK will not need to be assessed if a clinically meaningful increase in MK-8189 exposure is not observed in moderate hepatic impairment patients. Following enrollment of the moderate hepatic cohort, a control group will be enrolled with demographics which are reasonably matched to the mean demographic parameters to control for the influence of covariates. The Child-Pugh classification will be used to categorize hepatic impairment due to its widespread use and acceptance by regulatory agencies including the U.S. Food and Drug Administration [S 2003] and the European Committee for Medicinal Products for Human Use). [Guideline on the evaluation of... 2005]

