### **5 STUDY POPULATION**

In Part 1 male and female participants with moderate hepatic impairment and healthy participants between the ages of 18 and 75 years of age may be enrolled. If Part 2 is conducted, male and female participants with mild hepatic impairment between the ages of 18 and 75 will be enrolled.

The individual age and weight of the healthy participants is aimed to be within the range  $\pm$  15 years and  $\pm$  20% of the mean age and weight of participants with moderate hepatic impairment. In addition, the numbers of males and females of the healthy participants will be generally matched to the numbers of hepatic insufficient participants within  $\pm$  1; i.e., if there are 4 males and 4 females in the hepatic insufficient group, every effort will be made to ensure a 4:4 ratio in the healthy participants, but 3:5 or 5:3 would be acceptable as well.

Prospective approval of protocol deviations to recruitment and enrollment criteria, also known as protocol waivers or exemptions, is not permitted.

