#### **Demographics**

7. Is male or female, from 18 years to 75 years of age inclusive, at the time of signing the informed consent.

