## 6.3 Measures to Minimize Bias: Randomization and Blinding

### 6.3.1 Intervention Assignment

Participants will be assigned an AN for a single open-label treatment using the allocation schedule shown in [Table 2].

Table 2 Allocation of Participants to Treatment

Part 1a		
Hepatic Impairment Stage	N	Treatment
Moderate	$6 \leq n \leq 8$	MK-8189 4 mg
Healthy b	$6 \leq n \leq 8$	MK-8189 4 mg
Part 2a		
Mild	$6 \leq n \leq 8$	MK-8189 4 mg

a The participants in the groups defined by hepatic function should be reasonably similar to one another with respect to age, gender, and weight. However, participants with normal hepatic function should be matched at the group level. In order to make this matching possible, participants with normal hepatic function need to be enrolled after the participants with moderate hepatic impairment subjects have been recruited in Part 1. The participants with normal hepatic function in Part 1 also serve as control for mild hepatic category in Part 2.

b Participants with normal hepatic function are within  $\pm 15$  years of the mean age and within  $\pm 20\%$  of the mean weight for the moderate hepatic function group. In addition, the numbers of males and females of the healthy participants will be generally matched to the numbers of hepatic insufficient participants within  $\pm 1$ ; i.e., if there are 4 males and 4 females in the hepatic insufficient group, every effort will be made to ensure a 4:4 ratio in the healthy participants, but 3:5 or 5:3 would be acceptable as well

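### Does comparing the mild group with controls matched to the moderate group need its own tolerance or an adjusted GMR?

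*Combined protocol and SAP*

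**What the plan says.** Section 4.1 reuses the controls openly: "The healthy control group in Part 1 will be used for the PK comparison in Part 2". Footnote a of Table 2 (Section 6.3.1) repeats it: "The participants with normal hepatic function in Part 1 also serve as control for mild hepatic category in Part 2".

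The controls are selected to resemble the moderate group. Section 4.2 gives the purpose: "a control group will be enrolled with demographics which are reasonably matched to the mean demographic parameters to control for the influence of covariates". Section 5 sets a target window for each control of ±15 years in age and ±20% in weight, and it names the reference point: "of the mean age and weight of participants with moderate hepatic impairment". Sex counts are to agree within ±1. Footnote a fixes the order: "participants with normal hepatic function need to be enrolled after the participants with moderate hepatic impairment subjects have been recruited in Part 1". The control group is thus complete before any mild participant enters.

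For the mild group the plan has three provisions:

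- **Similarity rule.** Footnote a, attached to both the Part 1 and Part 2 headings of Table 2, says: "The participants in the groups defined by hepatic function should be reasonably similar to one another with respect to age, gender, and weight".
- **Age limit.** Section 5.1.2 has the same limit for mild and moderate participants: "Is male or female, from 18 years to 75 years of age inclusive, at the time of signing the informed consent".
- **BMI limit.** Section 5.1.2 requires a BMI of 18.5 to 40 kg/m² of both groups.

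Sections 9.1 and 9.6 fit population as the only fixed effect, on data pooled over both parts. Section 9.6 makes plots of PK against age and body weight optional.

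**The concern.** The study is not randomized, and the plan relies on matching to handle covariates. For the moderate/healthy comparison that matching has numbers. For the mild/healthy comparison it has only a qualitative request, and the model does not take over the task. The mild/healthy GMR for AUC0-inf and Cmax is the primary Part 2 estimate (Section 9.3). If the mild participants turned out lighter, heavier, older or younger than the controls, the difference would pass into that GMR, and the 90% CI, which reflects random error only, would not show it. The natural remedies look cheap: give the mild group a stated tolerance, and plan one supportive GMR adjusted for weight and age, which are already collected.

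**Working it through.** **1. The plan's own precision (Section 9.9).** Inputs: pooled SD 0.29 on the log scale, n = 6 per group, 90% two-sided CI. Half-width = t(0.95; 10) × 0.29 × √(2/6) = 1.812 × 0.1674 = 0.303, and exp(0.303) = 1.35. With an observed GMR of 1.50 the limits are 1.11 and 2.03. This reproduces the stated 0.30, 1.35, and 1.11 to 2.03.

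**2. How large could the distortion be?** The documents give no covariate effect and no expected mild-versus-control difference. As an assumption, let CL/F be proportional to weight^k with k from 0 to 1. If r is the ratio of mean weights (mild/healthy), the AUC GMR is multiplied by r^(−k).

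| r | multiplier, k = 0 to 1 |
|---|---|
| 0.8 | 1.00 to 1.25 |
| 0.9 | 1.00 to 1.11 |
| 1.1 | 1.00 to 0.91 |
| 1.2 | 1.00 to 0.83 |

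Every range includes no effect, and the extremes lie inside ×/÷1.35. Cmax is not quantified. The BMI limits (40/18.5 = 2.16-fold in weight at a given height) describe the most extreme pair of individuals. They say nothing about how far two group means would differ.

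**3. What would a copied tolerance do?** Suppose each mild participant had to be within ±20% of the healthy mean weight. The mild mean could still be 20% off, which is r = 0.8 or 1.2 and gives the same 1.25 or 0.83 at k = 1. The Part 1 window has the same property. If all controls sat at one edge, the moderate/healthy weight ratio would be 1/0.8 = 1.25 or 1/1.2 = 0.83, and the multiplier at k = 1 would be 0.80 or 1.20. The numeric window therefore does not hold Part 1 to a clearly stricter standard on means.

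**4. What would an adjusted GMR cost?** Take three pooled groups with a common SD of 0.29 (for the mild group an assumption) and no reduction of the residual SD by the covariates.

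- Unadjusted, n = 6: 1.753 × 0.1674 = 0.294. n = 8: 1.721 × 0.145 = 0.250.
- Weight and age, chance imbalance only: variance inflation 1 + 2/[3(n−1) − 3]. n = 6: 1.167, 13 df, half-width 0.320. n = 8: 1.111, 19 df, half-width 0.264.
- Weight only, real 20% shift: inflation 1 + {d²/[3(n−1)s²]}/(2/n), with d = ln 0.8 = −0.223 and s the within-group SD of ln(weight), assumed 0.20 or 0.10. n = 6 (14 df): inflation 1.25 or 2.00, half-width 0.330 or 0.417. n = 8 (20 df): 1.24 or 1.95, half-width 0.278 or 0.349.

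Section 9.6 plans unequal variances with Kenward-Roger. I simulated that at n = 6 (500 runs) with SDs of 0.16 healthy, 0.39 moderate and 0.39 mild, the last being an assumption, and a first-order Kenward-Roger variance correction. The mean half-width was 0.32 unadjusted and 0.34 with two covariates under chance imbalance. With weight alone and a 20% shift it was 0.36 (s = 0.20) to 0.43 (s = 0.10). In that last case the adjusted interval is about a third wider (0.43/0.32 = 1.34).

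**The case for a change.** The best argument for a change is that the sponsor itself judged numbers to be needed for the moderate/healthy contrast, and the same logic applies to the mild group. The control means will be known before mild recruitment starts, so a target is easy to set. One model named in advance is also more credible than covariates picked after 6 to 8 values per group have been seen. Part 2 runs only when moderate impairment has raised exposure to a clinically meaningful degree, which is when the mild estimate counts.

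The facts behind this stand: there is no number for the mild group, no adjusted estimate, and the age and weight plots are only optional. The step to a needed change does not.

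- A copied individual window leaves the worst case in place (step 3). A check on means without a threshold is no more definite than footnote a.
- A weight-and-age model would impose common slopes on three groups of 6 to 8 and omit sex, which is one of the three matching factors. Ascites is a Child-Pugh component (Appendix 11), so weight in impaired participants may partly reflect the disease. That last point is my inference, but it means adjusting for weight is not clearly neutral.
- The adjusted result would be supportive only, so the primary GMR would not move.

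**Conclusion.** No change is called for. Reusing one control group is a stated and coherent trade-off. It spares a second set of healthy participants in a part that may never run, within a study that tests no hypothesis (Section 9.8). The mild group has a matching rule in footnote a, and its age, BMI and cirrhosis criteria are those of the moderate group on which the controls are centred. Sites and analysts can apply the rule sensibly, because the control means are known when mild participants are screened. The age and weight plots that Section 9.6 foresees would show any marked imbalance.

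The size of any distortion is unknown and may be zero. For a 20% difference in mean weight it is a factor of 0.83 to 1.25 on the AUC GMR, against a random-error factor of 1.35 at n = 6. This rests on the assumed weight exponent of 0 to 1. The precision figures rest on an SD for mild impairment that the documents do not give. The sponsor may choose to put a number on the similarity of the mild group's means and to make the age and weight plots definite. Either is optional tidying that the validity of the planned estimate does not depend on.

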### 4.2 Scientific Rationale for Study Design

A 2-part, open-label study design has been selected to evaluate the effect of hepatic impairment on the PK of MK-8189. Though hepatic elimination may be important for MK-8189, the magnitude of the preclinical and clinical safety margins support a reduced design with an evaluation of participants with moderate hepatic impairment first; in the clinic a

starting dose 2-fold and a top dose 12-fold the proposed dose have been evaluated and found to be generally well tolerated (Panel D, P007). It has been recognized that, in general, low clearance compounds ( $CL < 20$  L/h) are less affected by hepatic impairment [Heimbach, T., et al 2020]. Though MK-8189 is primarily eliminated through hepatic metabolism, the low clearance of MK-8189 ( $CL/F < 5$  L/hr) may limit the effect of moderate hepatic impairment on MK-8189 PK.

Following a review of the safety and PK data from moderately hepatic impaired patients and healthy control participants (Part 1), a decision will be made by the Sponsor whether to conduct Part 2 in mildly hepatic impaired participants. If a clinically meaningful increase in MK-8189 exposure is observed in participants with moderate hepatic impairment (Part 1) when compared to healthy participants, Part 2 will be initiated. The effect of mild hepatic impairment on MK-8189 PK will not need to be assessed if a clinically meaningful increase in MK-8189 exposure is not observed in moderate hepatic impairment patients. Following enrollment of the moderate hepatic cohort, a control group will be enrolled with demographics which are reasonably matched to the mean demographic parameters to control for the influence of covariates. The Child-Pugh classification will be used to categorize hepatic impairment due to its widespread use and acceptance by regulatory agencies including the U.S. Food and Drug Administration [S 2003] and the European Committee for Medicinal Products for Human Use). [Guideline on the evaluation of... 2005]

The Child classification, which should only be applied to patients with a diagnosis of hepatic cirrhosis, was initially used to assess the preoperative risk of patients with hepatic cirrhosis. The Child scale, as modified by Pugh, et al [Pugh, R. N. H., et al 1973] has been subsequently found useful in classifying a patient's level of hepatic impairment for PK studies. The Child-Pugh scale has been shown to correlate with hepatic (i.e., metabolic) clearance for several compounds. [S 2003]

In the current study, patients with chronic, stable hepatic impairment due to any etiology will be enrolled, and the Child-Pugh scale will be used to classify the severity of liver disease (see Child-Pugh classification of the severity of liver disease presented in Appendix 10.11). The Child-Pugh scale used in this trial takes into account the medications/treatments being used to treat complications of cirrhosis, in order to accurately describe the severity of encephalopathy and ascites [Garcia-Tsao, G., et al 2007]. Patients' scores of 5 to 6, 7 to 9, and 10 to 15 on this scale are classified as having mild, moderate, and severe hepatic failure, respectively.

In addition, as the laboratory parameters specified in the Child-Pugh scale (e.g., reduced serum albumin, increased serum bilirubin, and increased INR) may be better associated with the capacity of the liver to eliminate drugs, in comparison to ascites and encephalopathy, [Guideline on the evaluation of... 2005] at least four (4) patients with moderate hepatic impairment (Part 1 only) will be required to have a score of at least 2 on one of the laboratory parameters on the Child-Pugh scale.

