### 4.2.1.2 Pharmacokinetic Endpoints

An objective of this study is to characterize the PK of MK-8189 in participants with hepatic impairment. Therefore, individual plasma concentration and actual sample collection times of MK-8189 will be used to derive the PK parameter values such as AUC0-24, AUC0-inf, Cmax, Tmax, C24hr, CL/F, Vd/F and apparent t1/2. Protein binding for MK-8189 will also be analyzed. As MK-8189 is highly protein bound, the fraction unbound PK parameters (at a minimum CL/F, Vd/F) will be provided in healthy participants and participants with hepatic impairment.

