#### **4.3 Justification for Dose**

A single-dose of 4 mg will be administered in this trial. The highest likely clinical dose of MK-8189 is expected to be 24 mg. While multiple doses up to 48 mg of MK-8189 have been found to be generally well tolerated, a titration scheme has been used to step up to this supratherapeutic dose. The titration approach has been used to mitigate dystonia which was observed in P001 with an immediate release formulation and the need to continue the titration approach with the CR formulation has not yet been evaluated. To date, the highest generally well tolerated starting dose evaluated is 8 mg, providing a 2-fold clinical margin to the 4 mg dose to be administered in this trial. While hepatic impairment may increase the exposure of MK-8189, this effect may be modest due to its low intrinsic clearance [Heimbach, T., et al 2020]. MK-8189 is a BCS class 1 compound up to doses of 16 mg and BCS class 2 at 24 mg. In addition, PK of MK-8189 generally increases dose proportionally in subjects with schizophrenia over the dose range evaluated (2 mg to 48 mg). Thus, the effect of hepatic impairment at a low dose of 4 mg is expected to be extrapolatable, within reasonable variability, to the highest likely clinical dose of 24 mg.

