## 9.6 Statistical Methods

### Pharmacokinetics:

At the end of the study, the final analysis will be run on pooled data from both study parts (if both parts are conducted).

Separately for each PK parameter, individual values of AUC0-24, Cmax, C24, AUC0-last, and AUC0-inf will be natural log-transformed and evaluated with a linear fixed effects model containing a fixed effect for population (each hepatic impairment group, and normal hepatic function). An unstructured covariance matrix will be used to allow for unequal population variances via the REPEATED and GROUP statement in SAS PROC MIXED. Kenward and Roger's method will be used to calculate the denominator degrees of freedom for the fixed effect (DDFM=KR). Ninety-five percent (95%) CIs for the least squares means for each population will be constructed on the natural log scale and will reference the t-distribution. Exponentiating the least-squares means and their corresponding 95% CIs will yield estimates for the population geometric means and confidence intervals about the geometric means on the original scale. Sample SAS code is given below:

```
proc mixed data=data;
  class population;
  model lnpk = population /ddf=kr;
  repeated/ group= population;
  lsmeans population /cl alpha=0.05;
run;
```

To compare participants in each hepatic impairment population to participants with normal hepatic function, a two sided 90% confidence interval for the true difference in means (hepatic impairment – normal hepatic function) will be calculated for AUC0-24, Cmax, AUC0-last, and AUC0-inf using the mean square error from the model and referencing a t-distribution. These confidence limits will be exponentiated to obtain the 90% confidence interval for the true ratio of geometric means (hepatic impairment/normal hepatic function) for each PK parameter and each hepatic population.

Figures showing individual PK values with GMs (95% CIs) by population, plotted on the natural log scale, will be provided for PK parameters AUC0-24, Cmax, AUC0-last, and AUC0-inf. A figure showing the GMR (hepatic impairment/normal hepatic function) and corresponding 90% CI will be provided for PK parameters AUC0-24, Cmax, AUC0-last, and AUC0-inf.

The above analyses will be carried out for PK calculated from both total and unbound concentrations.

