## 9.7 Interim Analyses

A preliminary analysis of Part 1 data may be conducted to inform on whether the study will proceed to Part 2.

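### Should Part 2 be waived only when the upper 90% confidence limit from Part 1 excludes a clinically meaningful increase?

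*Combined protocol and SAP*

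**What the plan says.** Section 4.1 makes Part 2 follow from a review of the Part 1 safety and PK data: "if there is a clinically meaningful higher exposure of MK-8189 in participants with hepatic impairment as compared to healthy participants, Part 2 will be conducted". Section 4.2 repeats the trigger, gives the decision to the sponsor, and adds the converse, that the effect of mild impairment "will not need to be assessed if a clinically meaningful increase in MK-8189 exposure is not observed in moderate hepatic impairment patients". Section 9.7 says: "A preliminary analysis of Part 1 data may be conducted to inform on whether the study will proceed to Part 2".

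The supplied text gives no numerical threshold. It does not say whether a point estimate or a confidence limit decides, or which of AUC0-inf and Cmax counts.

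Section 9.6 plans a two-sided 90% confidence interval for each GMR under a model with unequal variances, and adds: "The above analyses will be carried out for PK calculated from both total and unbound concentrations". Section 4.2.1.2 gives the reason for the unbound parameters: "As MK-8189 is highly protein bound, the fraction unbound PK parameters (at a minimum CL/F, Vd/F) will be provided". Section 9.9 gives the expected precision with 6 per group: a factor of 1.35 either way, so that an observed AUC0-inf ratio of 1.50 carries an interval of 1.11 to 2.03. Section 9.8 notes that nothing is tested.

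**The concern.** The reduced design rests on an inference: if moderate impairment does not matter, mild impairment need not be studied. That inference is safe if a meaningful increase has been ruled out. It is weaker if the increase merely failed to show in a small sample.

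The plan's own example seems to make the point. Section 4.3 says "the highest generally well tolerated starting dose evaluated is 8 mg, providing a 2-fold clinical margin to the 4 mg dose", and also that "multiple doses up to 48 mg of MK-8189 have been found to be generally well tolerated", which against the expected top clinical dose of 24 mg is again 2-fold. It adds that "the effect of hepatic impairment at a low dose of 4 mg is expected to be extrapolatable" to that dose. An observed ratio of 1.50 would not look like a 2-fold increase, yet its interval reaches 2.03.

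Section 4.2 also does not say whether exposure means total or unbound drug. If binding falls in liver disease, total AUC understates the unbound increase.

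At stake is whether mild impairment is studied at all. The Part 1 estimates are the same either way, but they cannot supply data in mild impairment.

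**Working it through.** **Inputs.** Section 9.9: between-subject SDs on the log scale of 0.39 (assumed for moderate impairment) and 0.16 (healthy), pooled 0.29; n = 6 to 8 per group. Section 9.6: two-sided 90% interval, unequal variances. The threshold M is not in the documents, so 1.25, 1.5 and 2.0 are assumed values.

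**1. The plan's own figure.** Half-width = t(0.95, 10) × 0.29 × √(2/6) = 1.812 × 0.29 × 0.577 = 0.3035, a factor of 1.35. Then 1.50/1.3545 = 1.11 and 1.50 × 1.3545 = 2.03. It reproduces.

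**2. The planned unequal-variance form.** SE = √((0.39² + 0.16²)/n).
- n=6: SE 0.172, df 6.6, half-width 0.329, factor 1.39.
- n=8: SE 0.149, df 9.3, half-width 0.272, factor 1.31.

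**3. A rule that uses the observed ratio alone.** P(waive) = Φ(−ln k / SE), where k is the true ratio divided by M.
- k = 1.00: 50%, whatever n is.
- k = 1.10: 29% (n=6), 26% (n=8).
- k = 1.25: 10% (n=6), 7% (n=8).

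The 50% therefore belongs to any point-estimate rule and is not caused by the small groups. Sample size governs only how fast the error falls above the threshold.

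**4. A rule that requires the upper 90% limit to be below M.** At k = 1 the simulated waiver rate is 5.0% for both n (400,000 trials per n). By the plan's factor of 1.35 with n=6, a waiver then needs an observed ratio below 2.0/1.35 = 1.48, 1.5/1.35 = 1.11 or 1.25/1.35 = 0.93. At M = 1.25 the observed ratio would have to show a decrease.

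**5. What that rule costs.** Probability of running Part 2 when the true ratio is 1.0 (simulation). The last column requires total and unbound drug both to pass, with equal SDs and a correlation of 0.95 down to 0.5, both assumed.

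| M | n | Observed ratio, one analyte | Upper limit, one analyte | Upper limit, both analytes |
|---|---|---|---|---|
| 2.0 | 6 | about 0% | 3% | 4-5% |
| 2.0 | 8 | about 0% | 0.5% | 0.6-0.9% |
| 1.5 | 6 | 1% | 32% | 37-48% |
| 1.5 | 8 | 0.3% | 19% | 23-31% |
| 1.25 | 6 | 10% | 68% | 73-84% |
| 1.25 | 8 | 7% | 60% | 65-77% |

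Each such trial doses up to 8 more people with liver disease.

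**6. Total against unbound.** Section 2.2.2.1 gives a human unbound fraction of 4.0%. If it rose to 5% (assumed), a true 2.0-fold unbound increase would appear as 2.0/(5/4) = 1.60-fold in total AUC. With M = 2.0 and n=6, a total-only rule would then waive in 90% of trials on the observed ratio and in 32% on the upper limit. But Section 9.6 produces both sets of results, and no section restricts the decision to total drug.

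**The case for a change.** The strongest case for a change is that Part 2 is a yes/no decision even in an estimation study, and a wrong waiver leaves no data in mild impairment. With M = 2.0 and n=6, among trials waived on the observed ratio the 90% interval still includes 2.0 in 54%, 78% and 90% of cases when the true ratio is 1.5, 1.75 and 2.0. If the sponsor already has a more cautious rule in mind, writing it down costs little.

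The arithmetic stands, and so does the observation that no threshold is given. Four things weaken the step to a mandatory rule.

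- The criticised rule is an inference. Sections 4.1 and 4.2 describe a review of safety and PK data, and no section says the observed ratio decides. Nothing prevents the sponsor from weighing the planned intervals.
- The 2-fold figure in Section 4.3 is a tolerability margin for the starting dose. It is not called a clinically meaningful increase in exposure. The 48 mg dose was reached by titration, and Section 4.2 also cites a tolerated top dose 12 times the trial dose. The low cost seen at M = 2.0 cannot be assumed.
- A rule on AUC0-inf alone would leave out Cmax, the other primary endpoint, which the plan's broader term (exposure) can cover. A strict rule that starts Part 2 whenever the limit is not met would also need a safety exception, which the present review allows.
- The errors computed concern the moderate-impairment ratio. How often a meaningful increase in mild impairment would be missed has not been estimated.

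**Conclusion.** No change to the plan is needed. Sections 4.1, 4.2 and 9.7 leave out a detail (threshold, deciding parameter and statistic) that the sponsor can settle sensibly before it looks at the Part 1 PK results. The material for a careful decision is already planned: AUC0-inf and Cmax, total and unbound, each with a 90% interval, reviewed together with safety.

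An upper-limit rule is a trade-off. It lowers the waiver rate at the threshold from 50% to 5%. With n=6, both analytes and no true effect, it raises the chance of an unneeded Part 2 to between 4-5% (M = 2.0) and 73-84% (M = 1.25). Which error matters more depends on a clinical threshold that the supplied text does not state. The GMRs and intervals reported from Part 1 are unaffected in either case.

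These figures rest on the planning SDs of 0.39 and 0.16, log-normal AUC0-inf and assumed values of M; the two-analyte figures also assume equal SDs and a correlation of 0.5 to 0.95. The waiver rates are for a single parameter. If AUC0-inf and Cmax were both at their thresholds and either could trigger Part 2, the 50% would lie between 25% and 50%, depending on a non-negative correlation. Part of the background section and the Investigator's Brochure were not available, and either might define the criterion.
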